- a) To educate Tanglewood Trail program participants about the health benefits of consuming a variety of fruits and vegetables, being physically active, and dietary strategies that can help protect their health from environmental pollution.
- b) Assess self-reported behavior change, knowledge change, and change in physical measurements (see below), and level of physical activity.

3. **Study Design:** The sample population consists of a convenience sample that is participating in a prospective study. This study will focus on nonpregnant healthy adult (ages 18+) community members who walk the Tanglewood Trail on Saturdays, June-August 2017.

Any interested community members who are 18 years or older, nonpregnant and able to voluntarily give their consent are welcome to join the study. One hundred participants will be randomized into one of two groups – a walking group and a farmer's market group.

The fifty participants randomized into the walking group will meet at the Housing Authority at a designated time each Saturday. When they arrive, they will be signed in by a community leader and receive a farmer's market voucher (**see attached**) for \$10 along with education material (5 of the 13 Saturdays). They will walk as a group to the farmer's market and hand their voucher to the market manager, who will give them \$10 in tokens to purchase fruits and vegetables at the market. The voucher will have two sides: one side will ask participants what fruits and vegetables they ate the past week; the second side will ask participants to check off what fruits and vegetables they purchase at the market that day. They will turn this in as they leave the market. The fifty participants randomized into the farmer's market group will meet at the farmer's market and sign in with a UK employee. They will receive the same voucher and education materials and follow the same procedure as the walking group. Participants randomized into this group will be allowed to walk if they want; no one will be dissuaded from engaging in physical activity. However, in order to receive their voucher, it is not required for them to walk.

Three times per month participants will be presented with education material concerning phytonutrients, the importance of fruit and vegetable intake, and how these factors might protect them from environmental pollutants. The education materials will be in the form of a.) a handout based on the Transtheoretical Model

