Form B: Medical IRB Research Description

(see attached example) or b.) Plate it Up Kentucky Proud recipe samples and cards (see attached example). A Registered Dietitian will be available to answer nutrition-based health questions once per month.

No participants will receive medications – neither real nor placebo.

Data will be a time series collection of finger-stick total cholesterol, LDL, HDL, triglycerides, hemoglobin A1c (cardiocheck meter), height, weight, waist circumference, carotenoid status (carotenoid RS, which is a non-invasive instrument that is a reliable indicator of fruit and vegetable intake (see attached), and a survey (see attached). Measurements will be taken twice – baseline data will be collected in May 2017, with follow-up data collected in early September 2017.

Finger stick tests will be conducted by University of Kentucky employees who have completed all necessary biohazard training (see attached IBC approval and certificates of completion). Lysol wipes will be available to wipe down equipment as needed. Hand sanitizer will be provided to each researcher to use between glove changes. Gloves will be changed between each participant. Heat packets will be available for participants with cold hands to make the finger stick go faster and easier. Lancets will be used to take the finger stick and all materials will be disposed of in sharps containers. All sharps containers will remain sealed until the research team returns to the University of Kentucky that same day to dispose of the sharps containers.

4. **Study Population:** Based on walking group numbers from summer 2016 we anticipate a maximum enrollment of 100 participants (18+ years old, nonpregnant). Previous research in Letcher County suggests the majority of participants will be white, ages 18-65, both male and female, of moderate health status. A prerequisite for participating in this study is the ability to walk approximately 1 kilometer to the Farmer's Market, nonpregnant, pre-supposing a baseline health status. Any interested community members over the age of 18 and in moderate or good health will be included. Since our focus is on changes in rates of chronic disease in adulthood, children will be excluded from study participation (but may walk the trail with their parents). Institutionalized adults, pregnant adults adults with impaired consent capacity, and prisoners will be excluded. No one will be excluded based on sex/gender or racial/ethnic identity.

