Finger stick tests will be conducted by University of Kentucky employees who have completed all necessary biohazard training. Lysol wipes will be available to wipe down equipment as needed. Hand sanitizer will be provided to each researcher to use between glove changes. Gloves will be changed between each participant. Heat packets will be available for participants with cold hands to make the finger stick go faster and easier. Lancets will be used to take the finger stick and all materials will be disposed of in sharps containers. All sharps containers will remain sealed until the research team returns to the University of Kentucky that same day to dispose of the sharps containers.

11. Benefit vs. Risk: Potential benefits include (but are not limited to) a decreased risk for high blood pressure, high blood glucose, and cardiovascular disease; a decrease in oxidative stress; a decrease in generalized inflammation; an increase in community engagement; an increase in physical activity, and an increase in overall fruit and vegetable consumption.

There is no more than minimal risk to participants in this intervention with the benefits outweighing any risk. There is however, a potential risk of a breach in confidentiality, which is minimal due to the study being voluntary, removing the signed consent form/cover sheet from the coded pre/post surveys, deleting the document containing participant names and codes once the post-survey data has been coded, shredding the cover sheets attached to post-surveys with participants names, using a password protected computer, and storing any hard copies of study-related material in a locked drawer that is in a locked office.

12. Available Alternative Treatment(s): N/A

Form B: Medical IRB Research Description

13. **Research Materials, Records, and Privacy:** Participants will be asked to fill out two surveys (May and September 2017). The surveys contain questions about demographics, self-reported health, physical activity, fruit and vegetable consumption, and community engagement.

Participants will be asked to complete weekly shopping cards that will require them to mark which fruits and vegetables they purchased at the farmer's market and what fruits and vegetables they ate over the past week.

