Participants will be asked for finger-stick total cholesterol, LDL, HDL, triglycerides, hemoglobin A1c (cardio check meter), height, weight, waist circumference, and carotenoid status (carotenoid RS, which is a non-invasive instrument that is a reliable indicator of fruit and vegetable intake) twice (May and September 2017).

The collected data will be collated and summarized without identification or attribution to the individual participants. All reports will only reveal aggregated summaries across participants. The surveys with attached consent forms will be collected and stored separately in a locked drawer in the PI's locked office. An electronic document containing participant name and code will be generated and stored on a password protected computer. Following the collection of post-survey data and coding of the post-survey data the electronic document containing the names and codes will be deleted. To minimize risk of identification the consent forms will be removed from the survey and the survey will have a code written on it. The consent forms, shopping cards and surveys will not be stored together, but both will be in a locked drawer.

The information collected will be used to assess whether walking 1 kilometer to the farmer's market and spending approximately \$10 at the market improves physical activity, fruit and vegetable intake, community engagement, and chronic disease-related biomarkers (i.e. cholesterol, A1c, etc).

14. **Confidentiality:** The collated data will only reveal summarized data without identifiable information. The de-identified data will be available electronically and stored on a password protected computer. The electronic document containing names with respective survey codes will be deleted after post-survey data has been collected and therefore will not be stored. The list will be deleted by January 2020. Any study materials and raw data will be retained for 6 years in a locked drawer within a locked office or on a password protected computer. The PI and program manager assigned to the project and involved in data collection will have access to these items.
15. **Payment:** Participants will be offered a farmer's market t-shirt at the baseline data collection time (May 2017) and a \$10 gift card at post-data collection (September 2017) as well as the weekly \$10 voucher to the farmer's market.
16. **Costs to Subjects:** N/A
17. **Data and Safety Monitoring:** N/A the study does not have greater than minimal risk.

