18. **Subject Complaints:** Participants can voice their concerns to the PI, Co-PIs, program manager, or the Office of Research Integrity, which is listed on the consent form.
19. **Research Involving Non-English Speaking Subjects or Subjects from a Foreign Culture:** N/A
20. **HIV/AIDS Research:** N/A
21. **PI-Sponsored FDA-Regulated Research:** N/A

Tanglewood Trail Walking Program in Rural Kentucky 2020 - SAP

A dependent t-test will be used for the difference in survey questions (environmental pollution knowledge, fruit and vegetable intake, and physical activity) between before and after the Tanglewood trail walking program.

When the sample size is 50, a dependent t-test with a 5% two-sided significance level will have 80% power to detect an effect size of 0.4 calculated from previous data.

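### The SAP judges fruit and vegetable intake only by a before/after test on survey answers, and omits both the carotenoid scan taken at the same two times and the comparison between randomised groups

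*Combined protocol and SAP*

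**What the plan says.** The SAP contains one analysis: "A dependent t-test will be used for the difference in survey questions (environmental pollution knowledge, fruit and vegetable intake, and physical activity", with the difference taken "between before and after the Tanglewood trail walking program". It has no group term and mentions no biomarker. Its power statement belongs to the same test and takes 50 as the number analysed: "a dependent t-test with a 5% two-sided significance level will have 80% power to detect an effect size of 0.4".

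The protocol measures intake in a second way. Section 3 (Study Design) describes the carotenoid scan as one "which is a non-invasive instrument that is a reliable indicator of fruit and vegetable intake". Section 13 schedules "carotenoid status (carotenoid RS, which is a non-invasive instrument that is a reliable indicator of fruit and vegetable intake) twice (May and September 2017" and gives the surveys the same timing: "Participants will be asked to fill out two surveys (May and September 2017". Section 1 (Background) lists fruit and vegetable intake and carotenoid status as separate outcomes. It states the hypothesis as a gain over the group that receives vouchers only. Objective (b) in Section 2 is to "Assess self-reported behavior change, knowledge change, and change in physical measurements".

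On what happens between the two surveys:
- Teaching participants about the benefits of produce is objective (a).
- Education recurs through the summer in both groups (Sections 3 and 7).
- Both groups fill in a card on the produce they ate in the past week and bought that day. Section 13 makes it weekly, and Section 5 gives it a place for the name.
- Section 8 makes the principal investigator, program manager and research assistant responsible for data collection. It has the latter two develop the education material, with the principal investigator overseeing.

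**The concern.** A survey answer moves for two reasons: the person eats differently, or the person reports the same diet differently. After a summer of being taught that produce matters and being asked about it repeatedly, an upward shift in reporting is plausible. The September survey also goes back to the team responsible for the teaching. A paired t-test sees only the mean difference and cannot separate the two causes.

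Under the SAP as written, a significant rise in survey answers could be reported as a rise in intake. Yet a measure that does not depend on participants' answers, taken at the same two times, would go unanalysed. The randomised comparison, in which a shift common to both groups would largely cancel, would also go unused.

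**Working it through.** **Step 1. What is measured and what is analysed.**

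| Measure | May and September? | In the hypothesis? | In the SAP? |
|---|---|---|---|
| Survey fruit and vegetable intake | Yes (Section 13) | Yes (Section 1) | Yes, before/after only |
| Carotenoid score | Yes (Sections 3 and 13) | Yes (Section 1) | No |
| Difference between groups in change, either measure | Obtainable from the above | Yes (Section 1) | No |

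The gap is in the analysis plan, not in data collection.

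**Step 2. The plan's own power figure.** Inputs from the SAP: n = 50 pairs, effect size d = 0.4, two-sided 5%. The paired t statistic follows a noncentral t distribution with n − 1 = 49 degrees of freedom and noncentrality d√n = 0.4 × √50 = 2.83. Power is 79.2%. The normal approximation gives 80.7%. The stated 80% is reproduced and is not in dispute.

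**Step 3. A reporting shift with no dietary change.** Let b be the mean reporting shift in SD units of the change score. The documents give no value, so the range is assumed. With a true change of zero, the chance of a significant result comes from the same formula with noncentrality b√50:

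| b (assumed) | b√50 | Significant, 50 pairs | Significant, 100 pairs |
|---|---|---|---|
| 0 | 0 | 5.0% | 5.0% |
| 0.1 | 0.71 | 10.7% | 16.8% |
| 0.2 | 1.41 | 28.4% | 50.8% |
| 0.3 | 2.12 | 54.8% | 84.4% |
| 0.4 | 2.83 | 79.2% | 97.7% |

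The 100-pair column (noncentrality b√100) applies if both groups are pooled. The protocol randomises 100 people, 50 to each group, and the SAP does not say whose data its 50 pairs are. A pure reporting shift of 0.4 SD would be declared significant exactly as often as the true effect the study is sized for.

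**Step 4. The same shift in a between-group comparison.** Both groups receive the same vouchers, card and education. If each group's reporting shifts by b, the difference in mean change is b − b = 0 and the test keeps its 5% level. Only a difference in shift between groups remains. With 50 per group and equal SD of change, noncentrality is 5 × the difference (√(50/2) = 5). Differences of 0.1, 0.2 and 0.3 SD give a significant result 7.9%, 16.8% and 31.8% of the time.

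**Step 5. The price of that comparison.** For a true between-group difference of 0.4 SD in change, noncentrality is 5 × 0.4 = 2.0 and power is 50.8%. By the normal approximation, 80% power needs 2 × (1.96 + 0.84)² / 0.4² ≈ 98.1, so 99 per group.

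**The case against.** The strongest reply is that objective (b) explicitly includes self-reported behavior change, so a survey endpoint is what the study set out to assess. That stands, and the survey item should remain. It does not answer the whole point, because Sections 1 and 13 also speak of intake itself, and objective (b) lists physical measurements alongside self-report.

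A second reply is that the real defect is the missing group comparison, since a shared reporting shift would largely cancel there. This is right as far as it goes, and the fix includes that comparison. But the two groups differ only in the walk and the place of sign-in. The comparison therefore cannot show whether intake rose in both groups. For that question the scan is the only evidence that does not rest on participants' answers.

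Third, a carotenoid rise from May to September may itself be seasonal. This also stands. It is why a reader should not infer that a before/after carotenoid rise ought to decide the intake claim. The documents do not support such a rule: the comparison is uncontrolled, the protocol lists intake and carotenoid status as separate outcomes, and a carotenoid marker could miss a true rise in other produce.

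Fourth, the shift sizes are assumed, participants are told their answers will be reported only in aggregate, and the attached survey is not available to us. All true. The table shows how sensitive the test is to a shift, not that one occurs.

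Last, the SAP is headed 2020 and the protocol's schedule is for 2017. The only measurement schedule supplied has the scan at both visits, so the point holds, but the sponsor should confirm that it applies to the data the SAP covers.

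**Conclusion.** The concern holds as a cheap improvement to the SAP. The planned test cannot separate a change in diet from a change in reporting. If nothing changes in the diet and reporting shifts by 0.1 to 0.3 SD, it is significant about 11% to 55% of the time with 50 pairs, against the nominal 5%. This rests on 50 complete pairs and on the assumed range of shift. Upward is the plausible direction after a summer of produce education, but the documents establish neither direction nor size.

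Two further inferences should be avoided. The protocol does not ignore carotenoids: it measures them and puts them in the hypothesis, and only the SAP is silent. Nor is participants' knowledge of their own group, which Section 5 says they learn at baseline, the main mechanism, because both groups receive the same produce prompts.

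Two inconsistencies do not alter the conclusion but must be reconciled. Section 3 gives education on 5 of 13 Saturdays in one place and three times a month in another (the latter also in Section 7). Section 6 mentions a midline collection, while Sections 3 and 13 give two measurement times.

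**What to change.** Amend the SAP as follows:
- Add change in carotenoid score, May to September, as an objective intake outcome reported beside the survey item, each with a 95% confidence interval.
- For both measures, estimate the difference between the randomised groups in mean change, with a 95% confidence interval, and use it for the hypothesis of a gain over the voucher-only group.
- Present the before/after change in either measure as descriptive of the program period and open to seasonal effects.
- State in advance that if the survey item rises without support from the carotenoid score, the result will be described as a change in reported intake. The carotenoid score is supporting evidence, not a condition that must be met.
- Say whose data make up the 50 pairs.

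The cost is wording, since the schedule already has the scan at both times. The downsides should be stated. The carotenoid analysis has no stated power, because the documents give no SD or expected change for it. The scan reflects carotenoid-rich produce more than all produce. With 50 per group the between-group comparison has about 51% power for a difference of 0.4 SD in change, so its interval should be read for width as well as for whether it excludes zero.

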Form B: Medical IRB Research Description

1. **Background:** The Tanglewood Trail walking group is a community-initiated walking group, spontaneously established in summer 2016. Community members meet at the Housing Authority in Whitesburg, KY and walk the approximately 1 kilometer Tanglewood Trail connecting the Housing Authority to the Farmer's Market. Participation in the walking group is open to the public. Participants that walk to the Farmer's Market on Wednesday evenings receive a \$5 voucher to the Farmer's Market and a \$10 voucher on Saturdays during the season (June-October). Adults 18 years and older receive one voucher each time they walk. Currently, there is no evaluation of the walking group program beyond the community tracking the name, number of walkers, and the number of vouchers distributed to walkers on each Wednesday and Saturday. This program was initiated by community members and UK researchers were not involved with its creation or tracking any component of the program.

The current proposed study will target non-pregnant healthy, 18+ years old, community members who are willing and able to walk the Tanglewood Trail on Saturday mornings, June-August 2017. Community members will be randomized into a walking group and a farmers market group. Both groups will receive farmers market vouchers of equivalent value. One group will meet at the Housing Authority and walk to the farmers market to obtain their vouchers and the other group will obtain their farmers market voucher at the farmers market. Both groups are welcome to walk the Tanglewood Trail if they would like, however those that are randomized into the walking group are expected to walk. However, people are not forced to walk and have the option to refuse to walk. We hypothesize that adults who regularly attend the walking group and subsequently purchase fruits and vegetables at the Farmer's Market will experience an increase in physical activity, fruit and vegetable intake, and community engagement, and a decrease in anthropometrics and biomarkers associated with adulthood chronic disease (including cholesterol, hemoglobin A1c, blood pressure, carotenoid status, weight, and waist circumference) beyond that of the farmers market voucher group only.

2. **Objectives:**

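### The SAP plans only before-after tests on three survey topics, so the protocol's between-group hypothesis on nine outcomes has no planned test, and no outcome is named primary

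*Combined protocol and SAP*

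**What the plan says.** The hypothesis is in Section 1 (Background). It concerns "adults who regularly attend the walking group and subsequently purchase fruits and vegetables" at the market. Three outcomes are expected to rise: community engagement, activity, and how much fruit and vegetables people eat. The section also predicts "a decrease in anthropometrics and biomarkers associated with adulthood chronic disease (including cholesterol, hemoglobin A1c, blood pressure, carotenoid status, weight, and waist circumference". The comparator is explicit: these changes are to be "beyond that of the farmers market voucher group only".

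The design in Section 3 matches that hypothesis: "One hundred participants will be randomized into one of two groups", fifty in each. Of the farmers market group it says: "They will receive the same voucher and education materials and follow the same procedure as the walking group". Section 4 adds that "we anticipate a maximum enrollment of 100 participants".

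Objective (b) in Section 2 is looser and mentions no comparator: "Assess self-reported behavior change, knowledge change, and change in physical measurements (see below), and level of physical activity". Section 13 says the information will be used to judge whether walking to the market and spending the voucher improves activity, intake, community engagement and chronic-disease biomarkers.

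The whole SAP is two sentences. The first plans a dependent t-test for the "difference in survey questions (environmental pollution knowledge, fruit and vegetable intake, and physical activity) between before and after" the programme. The second says that a sample of 50 gives that test 80% power, at a two-sided 5% level, for an effect size of 0.4 taken from previous data. No other part of the documents plans a test, and no outcome is called primary anywhere.

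**The concern.** The trial is randomised to answer a between-group question, and the plan never uses the randomisation. Because both groups receive the same voucher and the same education, a change between May and September could come from the voucher, the education, the season or the walking. A paired test cannot tell these apart, whether it is run in one arm or in both arms pooled (the SAP does not say which). Comparing the randomised groups can.

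Two further things are at stake. Participants give finger-stick, blood pressure, body and carotenoid measurements for which no analysis is written down, so the analysis would be chosen later. And a reader may take the 80% power as the power to show a benefit of walking, which is not what it describes.

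**Working it through.** **1. Count of outcomes.** Section 1 lists three outcomes expected to rise (physical activity, intake, community engagement) and six grouped as decreases (cholesterol, hemoglobin A1c, blood pressure, carotenoid status, weight, waist circumference): 3 + 6 = 9. Cholesterol is counted once, although Sections 3 and 13 measure total cholesterol, LDL, HDL and triglycerides; counting these separately would widen the gap.

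| Outcome | In Section 1 hypothesis | Before-after test in SAP | Group comparison in SAP |
|---|---|---|---|
| Fruit and vegetable intake | yes | yes | no |
| Physical activity | yes | yes | no |
| Community engagement | yes | no | no |
| Cholesterol | yes | no | no |
| Hemoglobin A1c | yes | no | no |
| Blood pressure | yes | no | no |
| Carotenoid status | yes | no | no |
| Weight | yes | no | no |
| Waist circumference | yes | no | no |
| Environmental pollution knowledge | no | yes | no |

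Hypothesised outcomes with no planned test: 9 − 2 = 7. Hypothesised outcomes with a planned group comparison: 0 of 9.

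**2. The SAP's own power figure.** Inputs from the SAP: n = 50, effect 0.4, two-sided 5%. For a paired t-test, df = 50 − 1 = 49 and the noncentrality is 0.4 × √50 = 2.83. The noncentral t gives 79.2%; the normal approximation gives 80.7%. The stated 80% is ordinary rounding.

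**3. Power of the group comparison, unadjusted.** The documents give no between-group effect, so using 0.4 here is an assumption: the difference between groups in change, in change SD units. With 50 per arm (Section 3), df = 2 × 50 − 2 = 98 and the noncentrality is 0.4 × √(50/2) = 2.00. Power is 50.8%. A within-person change of 0.4 becomes a group difference of 0.4 only if the voucher group does not change at all.

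**4. Power with adjustment for the May value.** Let r be the May-September correlation, which the documents do not give; 0.3 to 0.7 is assumed. With equal variances σ² at both times, the SD of change is σ√(2(1 − r)) and the residual SD after adjustment is σ√(1 − r²). The answer depends on the scale in which 0.4 is expressed:

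- Change SD units, the natural scale for an effect size from a paired test: the adjusted effect is 0.4√(2(1 − r))/√(1 − r²) = 0.4/√((1 + r)/2).
- Follow-up SD units: the adjusted effect is 0.4/√(1 − r²).

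| Assumed r | Adjusted effect (change SD units) | Power, 50 per arm | Adjusted effect (follow-up SD units) | Power, 50 per arm |
|---|---|---|---|---|
| 0.3 | 0.496 | 69.0% | 0.419 | 54.6% |
| 0.5 | 0.462 | 62.8% | 0.462 | 62.8% |
| 0.7 | 0.434 | 57.5% | 0.560 | 79.2% |

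On the change scale, power falls as the correlation rises; on the follow-up scale it rises. The scale has to be stated with any such figure.

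**The case against.** Four points can be made on the other side.

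- **The SAP may cover something else.** It is headed 2020, while the protocol describes May to September 2017. It mentions no randomisation, groups, vouchers or biomarkers; its n is 50, not 100; and its first topic, pollution knowledge, is missing from the survey content listed in Section 13. It could describe a later run of the programme. Against this, objective (b) does include knowledge change, and no other SAP is supplied. The reading is possible but not shown, so the first step must be to ask.
- **Objective (b) asks only for change.** This stands in part: the paired tests do serve the survey part of (b). They do not serve its physical-measurement part, and they do not test the Section 1 hypothesis.
- **The hypothesis is worded for regular attenders.** True, but its comparator is still the voucher-only group, so a before-after test does not answer it either.
- **The power illustrations rest on assumed inputs.** Correct. The documents fix no between-group effect, SD, correlation or dropout rate. The finding does not depend on these figures; they only show that the 80% does not carry over.

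A reader might go further and infer any of three things that the documents do not support. The first is that the power calculation is wrong: it reproduces for the test it names. The second is that the trial is shown to be underpowered: that would need a between-group effect, and none is given. The third is that outcomes were picked after the data were seen: the heading says 2020, but the documents do not say when the SAP was written.

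**Conclusion.** The gap is real and follows from the text alone. If the SAP is meant for the randomised trial in the protocol, following it as written tests none of the nine hypothesised outcomes between groups, leaves seven with no test, and names no primary outcome. The design and the planned measurements do support the right comparison; what is missing is the analysis plan for it.

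The 80% power is sound only for a within-person change in 50 people. If the between-group difference is assumed to be 0.4 change SDs with all 50 per arm analysed, power is about 51% unadjusted, and about 69% down to 57% with baseline adjustment as r goes from 0.3 to 0.7. If 0.4 is instead in follow-up SD units, the adjusted range is 55% up to 79%. It would be a misreading to take 79% as showing that adjustment restores the stated power: that figure needs both the follow-up scale and the top of the assumed correlation range. Losses before September would lower all of these.

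**What to change.** 1. Confirm that the SAP headed 2020 covers the randomised 2017 study in the protocol. If it covers another run, say so and supply the plan for this one.
2. If it does cover this study, make the main analysis of the Section 1 hypothesis a comparison of the groups as randomised, for each of the nine outcomes, with the September value adjusted for the May value. Use a model suited to each survey scale; the survey is an attachment not seen here.
3. Name one primary outcome before results by group are seen, and label the rest secondary or exploratory. If results by group have already been seen, label all nine exploratory.
4. Keep the paired tests as descriptive analyses of objective (b).
5. State that the 80% power applies to the within-person test only. Give the power of the group comparison with its assumed effect, scale, correlation and number analysed.

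The cost is SAP wording and a few more regressions on measurements already planned. The downside is a less favourable stated power.

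Two separate editorial points. Section 1 places carotenoid status among the decreases, which conflicts with the hypothesised rise in intake, given that Sections 3 and 13 call it an indicator of intake. Section 6 refers to midline data, which should be reconciled with the two time points in Sections 3 and 13.
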